4.1 Objectives, Endpoints and Assessment Methods

Objectives	Endpoints	Assessment
Primary		
 Immunogenicity To demonstrate the non- inferiority of the antibody response in terms of seroconversion rate 28 days after vaccine administration of one dose of vYF (administered on D01) compared to the antibody response after one dose of the YF-VAX control vaccine (administered on D01) in YF-naïve participants*. 	 Seroconversion rates will be assessed 28 days post-vYF (administered on D01) and post- YF-VAX (administered on D01) in a YF MN assay in YF-naïve participants Seroconversion is defined as a 4-fold increase in NAb titers as compared to the pre-vaccination value. With a nominal value of half LLOQ, ie, 5 (1/dil), assigned to baseline YF seronegative participants, the seroconversion requires an increase to at least a titer of 20 (1/dil) on 28 days post-vaccination. 	See Section 8.1.2 of the protocol.
Secondary		
 Immunogenicity To demonstrate the non- inferiority of the antibody response in terms of seroconversion rate 28 days after vaccine administration of one dose of vYF (administered on D01) compared to the antibody response after one dose of the YF-VAX control vaccine (administered on D01) in YF-naïve participants with a time window of +3 days. 	 Seroconversion rates will be assessed 28 days (time window of +3 days) post-vYF (administered on D01) and post- YF-VAX (administered on D01) in a YF MN assay in YF-naïve participants 	See Section 8.1.2 of the protocol.
• To describe the immune response to YF in both vaccine groups using YF MN assays before (D01)	YF antibody assessments will be performed using YF MN assay as follows for each group:	

Objectives	Endpoints	Assessment
and after (D11 in a subset [†] only, D29, M6, and yearly from Y1 to Y5) vYF or	NAb titers on D01, D11 (subset only [†]), D29, M6, and yearly from Y1 to Y5	
YF-VAX administration	Derived endpoints are:	
	• Seroconversion rates: at D11 (subset only†) and D29, M6, and yearly from Y1 to Y5 Seroconversion is defined as a 4-fold increase in NAb titers: i) as compared to the D01 titers at each time point up to M6; ii) as compared to the last planned previous time point from Y1 onwards	
	• Seroprotection rates: participants with antibody titer ≥ 10 (1/dil) at baseline (D01), at D11 (subset only†), D29, M6, and yearly from Y1 to Y5	
	• Geometric means of the individual titer ratios (GMTRs) for D11/D01 (subset only†), D29/D01, M6/D01 and yearly ratios.	
	The corresponding parameters are seroconversion rate, seroprotection rate, GMT, and GMTR.	
	Seroprotection is defined as NAb titers \geq threshold of 10 (1/dil).	
	Data will be analyzed depending on FV immune status at baseline (YF-naïve and immune, FV-naïve and immune, dengue serotypes 1-4 naïve and immune, Zika- naïve and immune).	
• To describe the immune response to YF in both vaccine groups using YF MN assays between D01 and D29 using the D29 +3 days time window in YF-naïve participants.	 Seroconversion rates at D29 Seroprotection rates at baseline (D01) and at D29 Geometric means of the individual titers ratios for D29/D01 	
Safety		See section 8.2 of the protocol

Objectives			Endpoints	Assessment		
•	To describe the safety profile of vYF vaccine in comparison to the safety profile of the control YF- VAX To describe the safety of	•	Presence, nature (Medical Dictionary for Regulatory Activities [MedDRA] preferred term), duration, intensity and relationship to vaccination of any unsolicited systemic adverse events (AEs)			
	vaccination in all participants up to 28 days after vaccination	•	reported in the 30 minutes after vaccination Presence, time to onset, number of			
•	To describe all serious adverse events (SAEs) up to 6-month follow-up		days of presence, and intensity of solicited (pre-listed in the participant's diary and electronic case report form [eCRF]) injection			
•	To describe related SAEs and all deaths from D01 to		site reactions up to 7 days after vaccination			
•	To describe all AESIs up to 6-month after vaccination;	•	Presence, time to onset, number of days of presence, and intensity of solicited systemic reactions up to 14 days after vaccination			
•	To describe the biosafety profile of vYF in comparison to the biosafety profile of the control YF-VAX in a subset only	•	Presence, nature (MedDRA preferred term), time to onset, duration, intensity, and relationship to vaccination (for systemic AEs only) of unsolicited (spontaneously reported) AEs up to 28 days after vaccination and AESIs up to 6- months after vaccination			
		•	Presence of any serious adverse events (SAEs) including serious AESIs, up to 6-month after vaccination			
		•	Presence of related SAEs and all deaths from D01 to 5 years after vaccination			
		•	Hematology and biochemistry out- of-range test results at D01 and D11 in a subset only ⁺			
Ex	ploratory					
To stat and pop	describe the serological tus of FV infection (dengue d Zika) in the study pulation at baseline	•	NAb levels against FV infection (dengue and Zika) in a blood sample taken at baseline	See section 8.1.2 of the protocol		

AESI: adverse event of special interest; D: day; eCRF: electronic case report form; FV: flavivirus; GMT: geometric means titer; GMTR: geometric means titer ratio; M: month; MN; microneutralization; NAb: neutralizing antibody; Y: year; YF: yellow fever.

* YF-naïve participants (or negative) at baseline correspond to participants with no detectable YF antibody (Ab) titers before vaccination. YF seronegative at baseline is defined as a titer < LLOQ for the assay (any participant with a baseline titer \geq LLOQ will be eliminated from the primary analysis [Per-protocol analysis]).

LLOQ determined as 10 (1/dil), also defined the threshold of protection.

‡ The following AESIs have been defined for this clinical development program based upon the prior experience with YF vaccines:

Serious hypersensitivity/allergic reactions

• Organ failure/serious viscerotropic events

• Serious neurologic events

†A subset of the first 90 participants (60 participants in Group 1 and 30 participants in Group 2) enrolled at some sites will provide an additional post-vaccination blood sample on D11 to assess the immune response elicited by both vaccines in terms of NAb titers, and biological safety parameters on D01 and D11.

4.2 Derived Endpoints: Calculation Methods

4.2.1 Immunogenicity

4.2.1.1 Computed Values for Analysis

In order to appropriately manage extreme values (< lower limit of quantification [LLOQ] and \geq upper limit of quantification [ULOQ]) for analysis purposes, the following computational rule is applied to the values provided in the clinical database for each blood sample drawn:

- For the computation of GMTs, any titer reported as < LLOQ will be converted to a value of LLOQ/2.
- For calculation of proportion of participants with NAb titers ≥ threshold of 10 (1/dil), a titer reported as < LLOQ will be converted to a value of LLOQ/2.
- For calculating geometric mean of titer ratio (GMTR), < LLOQ will be converted to LLOQ/2 for a numerator and < LLOQ will be converted to LLOQ for a denominator. If both numerator and denominator are < LLOQ, then both will be converted in the same way so that titer ratio=1.
- Any titer reported as > ULOQ will be converted to ULOQ.

4.2.1.2 Seroprotection

See Section 4.1 (or Section 8.1.2 of the protocol).

4.2.1.3 Seroconversion

See Section 4.1 (or Section 8.1.2 of the protocol).

4.2.1.4 Baseline Serostatus

The baseline serostatus (eg, YF naïve participants and YF immune, Dengue naïve and Dengue immune, Zika naïve and Zika immune) is defined as the presence of antibodies (Abs) in the baseline blood sample collected at Visit 1 (V01) in the present study from all participants.

YF naïve participants are participants with baseline YF NAb value below the threshold for protection [< 10 (1/dil)]. If the NAb value is \geq 10 (1/dil) then the YF immune indicator will be "Immune". Otherwise the baseline YF serostatus will be classified as "Undetermined".

The serostatus of dengue is computed based on values of dengue NAb titers against each of the four serotypes at V01. If the NAb value is positive (≥ 10 [1/dil]) for any serotype, then the dengue immune indicator will be "Immune". Else if the NAb value is not positive (< 10 [1/dil) and non-missing for all four serotypes (ie, all of the titers planned to be measured at baseline must be available, and valid [not coded "NR" in the serology database] then the dengue immune indicator will be "Naive". Otherwise the baseline serostatus will be classified as "Undetermined".

Zika serostatus will be determined using a Zika microneutralization test for serum samples obtained at baseline. Zika immune samples were defined as having a Zika antibody titer of \geq 100 (1/dil) (1). If the NAb value is not positive (< 100 [1/dil]) and non-missing (ie, the titers planned to be measured at baseline must be available, and valid [not coded "NR" in the serology database]), then the Zika immune indicator will be "Naive". Otherwise the baseline Zika serostatus will be classified as "Undetermined".

Flavivirus immune participants at baseline are defined as participants either immune to YF or immune to Dengue or immune to Zika at baseline. Flavivirus naive participants at baseline are defined as participants naïve to YF and naive to Dengue and naive to Zika at baseline. Otherwise the baseline Flavivirus serostatus will be classified as "Undetermined".

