8.1.2.2 Immunogenicity Assessment Methods

YF MN Method Description (all Participants, visits V1 and V4 to V10 for the main cohort, and visits V1, V2, and V4 to V10 for the subset of participants)

YF NAb titers will be measured using a MN assay. Serial, 2-fold dilutions of serum to be tested (previously heat-inactivated) are mixed with a constant concentration of the YF vaccinal strain 17D. The mixtures are inoculated into wells of a 96-well microplate with permissive Vero cells

and incubated for 2 days. A reduction in virus infectivity (viral antigen production) due to neutralization by antibody present in serum samples is detected by enzyme linked immunosorbent assay (ELISA). After washing and fixation, YF viral antigen production in cells is detected by successive incubations with a flavivirus-specific mAb, horse radish peroxidase anti-mouse immunoglobulin G (IgG) conjugate, and a chromogenic substrate. The resulting optical density is measured using a microplate reader. The reduction in YF virus infectivity as compared to that in the virus control wells constitutes a positive neutralization reaction indicating the presence of NAbs in the serum sample. The method was qualified by assessing precision, specificity, LLOQ, and dilutability. To verify the LLOQ of 10, a panel of 17 additional human serum samples diluted in a negative serum targeting a titer of ½ of the LLOQ to exactly the LLOQ was tested 11 times by 2 qualified analysts in 2 independent assay runs. This data supports that the LLOQ of 10 was verified for the YFV MN assay and LOD can be considered as equivalent to LLOQ (LOD = LLOQ):

- LLOQ determined as 10 (1/dil) with the MN assay defines the threshold of protection; a subject presenting with detectable Ab (\ge LLOQ) is considered as protected against YF virus
- As LOD = LLOQ, YF-naïve population, or YF negative population, corresponds to participants with no pre-existing Ab titers ie, no detectable as below LLOQ equal to 1:10. Those participants are given a value equal to half LLOQ, ie, 5 (1/dil)
- Seroconversion is defined as having at least a 4-fold increase of Ab titers as compared to baseline (pre-vaccination value); Sanofi Pasteur would like to consider this 4-fold increase in Ab titers for both participants with or without pre-existing Ab titers:
 - For participants assigned with a value at baseline of 10 (LLOQ) or more, 1/dil, seroconversion means values of 40 (1/dil), or more post-vaccination.

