 - For participants with a nominal value of 5 (half LLOQ) 1/dil assigned to baseline YF seronegative participants, this means that seroconversion requires an increase to at least a titer of 20 (1/dil) on day 28 post-vaccination.

The assay was deemed suitable for its intended use to quantitate YF NAb in human serum. Laboratory technicians conducting the immunogenicity assays will be blinded to the group to which each participant was assigned.

The YF MN assay will be performed at Sanofi Pasteur GCI, Swiftwater, Pennsylvania, or at a qualified contract laboratory for GCI.

Zika MN method description (all participants, samples from V1)

Zika NAbs will be measured using a MN assay. Serial, 2-fold dilutions of serum to be tested (previously heat-inactivated) are mixed with a constant concentration of Zika virus. The mixtures are inoculated in duplicate into wells of a 96-well microplate with permissive Vero cells. After adsorption, cells are incubated for 4 days. A reduction in virus infectivity (viral antigen production) due to neutralization by antibody present in serum samples is detected by ELISA. After washing and fixation, Zika viral antigen production in cells is detected by successive incubations with flavivirus-specific mAb, horseradish peroxidase goat anti-mouse IgG conjugate, and a chromogenic substrate. The resulting optical density is measured using a microplate reader.

The reduction in Zika virus infectivity as compared to that in the virus control wells constitutes a positive neutralization reaction indicating the presence of NAbs in the serum sample (13). The LLOQ of the assay is 10 (1/dil).

Dengue PRNT method description (all participants, samples from V01)

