	Ratio V08 (V01+3Y)/ V07 (V01+2Y)	###	###.#	(###.#; ###.#)	###	###.#	(###.#; ###.#)	
	Ratio V09 (V01+4Y)/ V08 (V01+3Y)	###	###.#	(###.#; ###.#)	###	###.#	(###.#; ###.#)	
	Ratio V10 (V01+5Y)/ V09 (V01+4Y)	###	###.#	(###.#; ###.#)	###	###.#	(###.#; ###.#)	
Naïve								

Table 7.3: Summary of geometric means of titers and geometric means of individual titer ratios of antibody against YF virus by FV status at baseline - Microneutralization assays - Full Analysis Set

* Subset only

M: Number of participant s available for the endpoint

Flavivirus status: Immune for participants with quantified (\geq LLOQ) neutralizing Abs against YF, and/or against at least one dengue serotype, and/or Zika in the baseline sample; naive for participants without quantified (\leq LLOQ) neutralizing Abs against YF, with no Ab quantified against any of the four dengue serotypes and Zika in the baseline sample.

Table 7.4: Summary of percentages of participants achieving seroconversion after one dose YF vaccination by YF status at baseline - Microneutralization assays - Full Analysis Set

YF status Time point		vYFv (N=xxx)			YF-VAX (N=xxx)			
		Seroconversion rate			Seroconversion rate			
		n/M	(%)	95% CI	n/M	(%)	95% CI	
Immune	V02 (V01+10d)/ V01 (Pre-inj)	###/###	##.#	(##.#; ##.#)	###/###	##.#	(##.#; ##.#)	
	V04 (V01+28d)/ V01 (Pre-inj)	###/###	##.#	(##.#; ##.#)	###/###	##.#	(##.#; ##.#)	
	V05 (V01+6M)/ V01 (Pre-inj)	###/###	##.#	(##.#; ##.#)	###/###	##.#	(##.#; ##.#)	
	V06 (V01+1Y)/ V05 (V01+6M)	###/###	##.#	(##.#; ##.#)	###/###	##.#	(##.#; ##.#)	
	V07 (V01+2Y)/ V06 (V01+1Y)	###/###	##.#	(##.#; ##.#)	###/###	##.#	(##.#; ##.#)	
	V08 (V01+3Y)/ V07 (V01+2Y)	###/###	##.#	(##.#; ##.#)	###/###	##.#	(##.#; ##.#)	
	V09 (V01+4Y)/ V08 (V01+3Y)	###/###	##.#	(##.#; ##.#)	###/###	##.#	(##.#; ##.#)	
	V10 (V01+5Y)/ V09 (V01+4Y)	###/###	##.#	(##.#; ##.#)	###/###	##.#	(##.#; ##.#)	
Naive	•••						. , ,	

n: Number of participant s who achieve a yellow fever vaccination seroconversion.

M: Number of participant s with available data for the endpoint.

Seroconversion: For a participant with a fourfold increase in NAb titers as compared to the previous timepoint value

YF status: Immune for participants with quantified (\geq LLOQ) neutralizing Abs against YF; naive for participants without quantified (\leq LLOQ) neutralizing Abs against YF in the baseline sample.

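### SAP text classifies Zika immunity at 100 or more, but three table footnotes build flavivirus status on any titer at or above the LLOQ of 10; a seroconversion sentence in the protocol also needs correcting

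*SAP*

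**What the plan says.** **Zika and flavivirus status.** SAP 4.2.1.4 sets a cut-off specific to Zika and cites a reference for it: "Zika immune samples were defined as having a Zika antibody titer of" 100 (1/dil) or more. The naive side mirrors it: "If the NAb value is not positive (< 100 [1/dil]) and non-missing". YF and each dengue serotype are cut at 10. The combined status follows from these indicators: "Flavivirus immune participants at baseline are defined as participants either immune to YF or immune to Dengue or immune to Zika at baseline". FV-naive requires naive status on all three, and anything else is Undetermined.

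The footnotes of Tables 7.3, 7.5 and 7.7 in SAP Section 7 use another rule. FV-immune there means quantified (at or above LLOQ) "neutralizing Abs against YF, and/or against at least one dengue serotype, and/or Zika in the baseline sample". FV-naive means no quantified YF antibody and "with no Ab quantified against any of the four dengue serotypes and Zika in the baseline sample". There is no Undetermined class. For the Zika microneutralization assay, Protocol 8.1.2.2 gives "LLOQ of the assay is 10 (1/dil").

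**Seroconversion in YF-seropositive participants.** Protocol 8.1.2.2 gives the general rule: "Seroconversion is defined as having at least a 4-fold increase of Ab titers as compared to baseline", applied with or without pre-existing titers. A sub-bullet then says that for a baseline of 10 or more, "seroconversion means values of 40 (1/dil), or more post-vaccination". SAP 4.2.1.3 has no derivation of its own and refers to SAP 4.1 or, alternatively, to Protocol 8.1.2.

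**The concern.** SAP 5.1.2.2 asks for immunogenicity by YF serostatus and by FV serostatus. The FV split fills Tables 7.3, 7.5 and 7.7 and defines the populations of Figures 7.3 and 7.4. With two rules in one document, either the programming follows the text and the printed footnotes misdescribe the strata, or it follows the footnotes and the analysis departs from the derivation section. The FV-immune stratum should be thin. Known FV infection and prior FV vaccination are exclusions (Protocol 5.2), and Protocol 4.2 expects few FV-experienced participants. A handful of people changing stratum could visibly alter those rows and curves.

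The 40-or-more sentence raises a similar problem for YF-immune participants, whose seroconversion is a stated secondary evaluation (Protocol 4.2). Taken literally, it would count some participants with unchanged titers as responders.

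**Working it through.** **1. Zika cut-offs.** Inputs: immune at 100 or more (SAP 4.2.1.4); immune at or above LLOQ (footnotes of Tables 7.3, 7.5 and 7.7); Zika LLOQ = 10 (Protocol 8.1.2.2). The footnotes print LLOQ, not 10; the value comes from the protocol. For a participant negative for YF and all four dengue serotypes:

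| Baseline Zika titer (1/dil) | FV status, SAP 4.2.1.4 | FV status, footnotes |
|---|---|---|
| 5 (below LLOQ) | Naive | Naive |
| 10, 20, 40, 80, 99 | Naive | Immune |
| 100, 160 | Immune | Immune |

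The rules disagree for every titer from 10 to below 100. That is a 100/10 = 10-fold range, or log2(10) = 3.3 two-fold dilution steps. In this group the move is one-way: the footnotes make FV-immune some participants whom the text makes FV-naive. A participant already immune to YF or dengue is FV-immune under both rules.

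The missing Undetermined class is a second, smaller difference. A participant negative for YF and dengue with no valid Zika result is Undetermined under SAP 4.2.1.4, but could be read as naive under the footnotes because no Zika antibody was quantified.

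**2. How many participants.** The documents give no distribution of baseline Zika titers, so no count follows. For scale only, each 1% of the planned 570 with this pattern would be 0.01 x 570 = 5.7 participants. The true percentage may be zero.

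**3. Seroconversion threshold.** The seronegative figure reproduces: assigned baseline 5, and 4 x 5 = 20, as the protocol states. For seropositives, the titer needed is 4 x baseline, and the fold rise at the stated threshold is 40 / baseline:

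| Baseline | 4-fold rise needs | Fold change at a post-dose titer of 40 |
|---|---|---|
| 10 | 40 | 4 |
| 20 | 80 | 2 |
| 40 | 160 | 1 (no change) |
| 80 | 320 | 0.5 (a fall) |
| 160 | 640 | 0.25 (a fall) |

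The sentence is right at baseline 10 and wrong at every baseline above it. Read literally, anyone with a baseline of 40 or more whose titer does not change would count as seroconverted.

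**4. Which analyses use either rule.**
- Primary test: confined to YF-naive participants (baseline 5, threshold 20), with no selection on Zika. It uses neither rule. SAP 5.1.1.1 also names the Full Analysis Set for the primary analysis, but the objective there is still stated for YF-naive participants.
- The +3-day analysis on the sub-PPAS: a subset of the PPAS, so YF-naive only. It uses neither rule.
- Tables 7.2, 7.4 and 7.6 and Figures 7.1 and 7.2 (by YF status): unaffected by the Zika cut-off.
- Tables 7.3, 7.5 and 7.7 and Figures 7.3 and 7.4 (by FV status): affected by the Zika cut-off.
- Immune rows of Table 7.4, and YF-immune participants within Table 7.5: the only places where the 40-or-more sentence could matter.

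**The case against.** The strongest reply on Zika is that SAP 4.2.1.4 is the derivation section and is complete, while Section 7 describes itself as optional and says that the full shells are in a separate document. That makes it likely that the programming follows the text. It does not remove the contradiction. Section 7 is part of the SAP and presents its main outputs, and a footnote tells the reader how the strata were formed. If the text is followed, the footnote as printed is false.

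The reply on seroconversion is stronger. A reader might infer that 40 or more is the operative rule and that unchanged titers will be reported as vaccine responses. The documents do not support that. The sentence sits under a general statement of a 4-fold rise. SAP 4.2.1.3 names SAP 4.1 first, and SAP 4.1, SAP 5.1.2.2 and the footnotes of Tables 7.4 and 7.5 all require a 4-fold increase. The likeliest explanation is a loosely worded illustration of the baseline-10 case. What remains is that SAP 4.2.1.3 offers Protocol 8.1.2 as an equivalent source, and that fixed thresholds are familiar in this program: 20 for naive participants here, and 40 for naive participants in VYF01 (Protocol 2.1). The sentence should not be left as it stands.

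**Conclusion.** The Zika inconsistency is real and rests on the wording alone: participants negative for YF and dengue with Zika titers of 10 to 99 fall in opposite FV strata under the SAP's two definitions. The only inference needed is that LLOQ in the footnotes means the assay's stated LLOQ of 10 when applied to Zika.

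The seroconversion sentence is a secondary point. It is an internal contradiction in the protocol, correct only at baseline 10, and not the governing definition.

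The consequences are limited to descriptive secondary results. Two wider readings should be resisted. Neither issue touches the primary non-inferiority conclusion or the sub-PPAS analysis. Nor can any particular number of reclassified participants be claimed, because the documents contain no Zika titer data.

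**What to change.** 1. In the footnotes of Tables 7.3, 7.5 and 7.7, replace the definition with that of SAP 4.2.1.4. FV-immune is YF at least 10, or any dengue serotype at least 10, or Zika at least 100. FV-naive is naive on all three with valid results. Otherwise the status is Undetermined. SAP 4.2.1.4 is the one to keep because it is specific to Zika, cites a source and covers missing results.
2. Use the same strata for Figures 7.3 and 7.4. They carry no definition of their own, so a cross-reference to SAP 4.2.1.4 is enough.
3. In Protocol 8.1.2.2, replace the 40-or-more sentence with: at least 4 times the participant's own D01 titer (eg, 40 when baseline is 10). Limit this to D11, D29 and M6. From Y1 onwards keep the existing comparator, the last planned previous time point. If the protocol will not be amended, put the same sentence in SAP 4.2.1.3 in place of its reference to Protocol 8.1.2.

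The cost is wording only, with no new data or assays. The programmed FV and seroconversion derivations should be checked once against the corrected text.
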